14.9 Financial Disclosures

Assumed this is a sponsored study, after the IEC/IRB approval, the sponsor will put in place with the hospital administration of the site an agreement that will allow to pay the involved department for study execution. It is understood that, considering study procedures consist of a observational (prospective and retrospective) collection of clinical data, the sponsor will pay the time used by the Investigator to screen the eligible patients, as well as the time to fulfil and handle the clinical database.

14.10 Publication

The sponsor and the investigator intend to compile a comprehensive publication of study results in a peer review journal, appropriately addressing contributions of co-authors.

The sponsor recognizes the right and interest of co-authors, to scientifically publish the results obtained from the study for non-commercial purposes, even if the effects ascribed to the investigational product fail to materialize.

The sponsor, together with the investigator, reserves the right to publish and present the results of this study at scientific congresses, to submit these clinical trial data to national and international Regulatory Authorities, and to register the study in a publicly accessible database.

Prior to any publication or presentation of study results, co-authors may submit a manuscript/abstract of the intended publication or presentation to the sponsor for review. Proposals for changes and modifications raised by sponsor will be taken into consideration by the participating Investigators if such proposals do not interfere with the scientific nature and content of the publication.

The identity of the sponsor and the nature of his contribution to this study shall be disclosed in any publication or presentation.

1 GLOSSARY

Abbreviation	Explanation
AE	Adverse Event
CI	Confidence Interval
CRF	Case Report Form
CRO	Contract Research Organization
CV	Curriculum Vitae
DB	Database
IC	Informed Consent
ICH	International Conference on Harmonization of Technical Requirements for Registration of Pharmaceuticals for Human Use
IEC/IRB	Independent Ethics Committee/Institutional Review Board
JPS	JuniOrtho™ Plating System™
Max	Maximun
MDDs	Medical Device Deficiencies
Min	Minumun
PMCF	Post-Market Clinical Follow-up
QOL	Quality of Life
ROM	Range of Motion
SAE	Serious Adverse Event
SOA	State-of-art
WBI	Weight Baring Index

2 INTRODUCTION

A manufacturer of a medical device must demonstrate that the intended purpose(s) and claim(s) made in relation to safety and performance of a Medical Device are achieved. As a general rule, such demonstration will require clinical data. Clinical data is data which is relevant to the various aspects of the clinical safety and performance of the device. This may include data from prospective and retrospective clinical investigations of the device concerned as well as market experience of the same or equivalent devices and medical procedures and information from the scientific literature.

The aim of the present study is to collect post-market clinical evidence (post-market clinical follow up - PMCF) on the use of the medical device JuniOrtho Plating System (JPS).

2.1 BACKGROUND INFORMATION

Principles of bone fixation through plating systems Plating systems are treatment options for bone fixation, indeed they are intended to provide bone fragments stabilization in case of bone fracture or osteotomy. Fixation works by blocking movements that would prevent the normal biological process of callus formation and consolidation. Excessive movement would otherwise increase the incidence of delayed union or nonunion. The very same principle is exploited when surgical fusion of bone fragments is sought, for example in joint arthrodesis or after surgical osteotomies performed to correct a limb deformity.

The JPS is a complete plating system designed to address the specific demands of advanced deformity and trauma reconstruction of the lower extremities in pediatric population and small stature adults. The system is intended for internal fixation and stabilization of fractures, osteotomies, mal-unions and non-unions of long bones of the lower limb.

Indications (as per IFU)

The JPS is intended for internal fixation and stabilization of fractures, osteotomies, mal-unions and non-unions of long bones of the lower limb.

The JPS is indicated for internal fixation and stabilization of femoral and tibial fractures, osteotomies, mal-unions and non-unions. Indications include:

- Varus, valgus, rotational and/or shortening osteotomies
- Femoral neck and/or pertrochanteric fractures
- Proximal and distal metaphyseal fractures
- Pathological and impending pathological fractures

Use of the JPS JuniOrtho Plating System™ is indicated in pediatric (excluding newborns) and small stature adult patients.

2.2 RATIONALE OF THE CLINICAL INVESTIGATION AND JUSTIFICATION OF VULNERABLE GROUP

Orthofix Srl put the JPS on the European market (2019) by the mean of a pre-market clinical evaluation made under the Medical Device Directive (MDD) requirements that was based on the analysis of the scientific literature of equivalent devices.

This study has been planned as part of the Orthofix Srl post-market active surveillance plan for the collection of data on both the clinical performance and the safety profile of the JPS in a representative population of patients and users.

The rationale of the proposed study is to update and support the pre-market clinical evaluation of the JPS with real-word-evidence clinical data, in order to confirm the benefit/risk ratio of this medical device and to keep the CE mark under Medical Device Regulation (MDR) requirements.

The uniqueness of the pediatric population manifests itself in specific indications for lower extremity reconstruction, mostly due to congenital deformities or conditions; different approach in compliance with postoperative care or need for adaptability to rapid growth and development. The JuniOrtho™ Plating System™ (JPS) is a well established, marketed device, commercially available and used as standard device in orthopedic surgeries.

The post-marketing, retrospective/prospective study with CE-marked device JuniOrtho™ Plating System™ (JPS) is designed for gathering real-world medical data from treatment of congenital deformities and fractures in lower limb of pediatric and in small stature adult patients.

All data will be collected from standard medical documentation of patients who have already been treated with JPS. Additionally, all procedures that patients underwent are justified by standard of care.

Constant identification of serious or unexpected serious risk related to the use of the device, especially in real-world experience may bring additional data, that can contribute to the safety of future patients.

In conclusion, patients will not directly benefit from the participation in this study but no additional risk related to the study participation is to be recognized.

3 PROTOCOL AND CRF VERSION

Protocol version: Version3.1_21/06/2023

CRF version: v.96.11

4 OBJECTIVE AND DESIGN

5 OBJECTIVES OF THE ANALYSIS PLAN

The analysis plan proposed below describes the aspects needed to know about the study and the statistical analysis methods to be used to apply them to the data collected and respond to the study objectives.

6 PRIMARY STUDY OBJECTIVE

The primary objective of the study is to evaluate the safety profile of JPS within the scope of its intended purpose, when used according to the manufacturer IFU on a representative population of subjects and users.

In order to fulfill this objective, the safety profile of JPS will be assessed by the following endpoints:

- percentage (%) of subjects with at least one serious/not serious adverse event certainly related or possibly related to JPS (primary endpoint) at device removal followup (up to 18 months according to site's standard practice).
- percentage (%) of Medical Device Deficiencies (MDDs) at device removal follow-up (up to 18 months according to site's standard practice).

7 SECONDARY STUDY OBJECTIVES

The secondary objective of the study is to evaluate the clinical performance of JPS within the scope of its intended purpose, when used according to the manufacturer IFU on a representative population of subjects and users.

In order to fulfill these objectives the clinical performance of JPS will be assessed by the two following efficacy endpoints:

- percentage (%) of subjects that reached a satisfactory bone consolidation according to investigator's opinion.
- percentage (%) of subjects that maintained bone correction alignment according to investigator's opinion until device removal.

8 STUDY DESIGN

This is a Post Market Clinical Follow-up (PMCF) study which is retrospective and prospective, observational, single-center, not controlled. All data from patients observation are gathered according to the site standard-of-care.

9 STUDY POPULATION

This study will be conducted only on patients with a regular indication for JPS as per IFU (no off-label use will be included): the system is intended in pediatric (excluding newborns) and small stature adult patients. Pediatric patients include infants (greater than 1 month to 1 years of age), children (greater than 1 to 12 years of age) and adolescents (greater than 12 to 18 years of age) and appropriate adults (where according to investigator assessment, the JPS plates fit the treated bone anatomy).

This study includes only one site (monocentric) that is located in Wetter (Germany). The site was chosen for this study due to the number of subject devices already implanted, and the wideness of the indications covered by the surgeries. The site was also positively evaluated by sponsor for the appropriate qualification and competency of the investigator and of the staff, and availability of facilities and equipment.

Sample size calculation:

Assuming the expected proportion of patients with at least one serious/not serious adverse event surely or possibly related to JPS will be 3 %, and assuming the worst case of each patient contributing for only one JPS implant case: 30 subjects was calculated to be the sample size of this study so that the upper limit of the 95 % confidence interval for the primary endpoint, based on the exact binomial method, is under 15 %. Considering that one patient can contribute for one that one JPS implant, and considering a 10% drop out rate, the site can enrol a maximum of 40 JPS implant cases.

10 STUDY DURATION

The follow-up period considered for this study lasts until the second surgery for JPS removal that, with the exception of clinical complications, is usually scheduled between 9 and 18 months after the surgery. (see table 10.2 "Events and Assessments Schedule" in protocol).

The estimated length of data collection period by the investigator is the time until all data is abstracted from clinical records. The data extraction from clinical record will finish after the plate removal of the last patient is completed.

11 INCLUSION CRITERIA

A patient will be eligible for inclusion in the study if:

- had/has a regular indication for surgical intervention with JPS according to the manufacturer's IFU.
- underwent a surgery for bone deformity correction or trauma reconstruction of the lower extremities performed by JPS.
- the clinical data registered in her/him patient chart are sufficient to assess the safety and efficacy endpoint of the study (for retrospective patients).
- patient (or his/her legally acceptable representative) is capable of understanding the content and is willing to sign the Informed Consent Form (ICF).
- patient is willing and able to participate in the data collection and comply with the protocol requirements.

12 EXCLUSION CRITERIA

A Patient will be excluded from participation in the study if he/she:

- had/has a medical condition that is a contraindication according to the manufacturer's instruction for use leaflet.
- had/has a concomitant not permitted device which cannot be safely removed.
- patient for whom there are other concurrent medical or other conditions that in opinion of the participating investigator may prevent participation or otherwise render patient ineligible for the study.

13 ANALYSIS POPULATION

The classification of the implants based on compliance with the screening criteria is defined below:

- **Evaluable implants** are defined as all implants who meet all inclusion criteria and none of the exclusion criteria described in the protocol.
- **Non-evaluable implants** are defined as all implants who fail to meet any of the inclusion criteria or meet any of the exclusion criteria.

The CRF contains the screening criteria information in the form of a binary variable (Yes/No) for each item described.

Analyses will be performed on evaluable implants.

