6. STUDY OBJECTIVES

6.1 Primary Objective

The primary objective of the study is to evaluate the safety profile of JPS within the scope of its intended purpose, when used according to the manufacturer IFU on a representative population of subjects and users.

In order to fulfill this objective, the safety profile of JPS will be assessed by the following endpoints:

- percentage (%) of subjects with at least one serious/not serious adverse event certainly related or possibly related to JPS (primary endpoint) at device removal follow-up (up to 18 months according to site's standard practice);
- percentage (%) of Medical Device Deficiencies (MDDs) at device removal follow-up (up to 18 months according to site's standard practice).

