10.2 Description Event by Event

10.2.1 V0: Screening and Baseline

Prospective patients who meet the eligibility criteria will be enrolled in the study. Patients who agree to enter the study must sign the approved Informed Consent Form. Consented patients will have performed assessments as outlined in this protocol.

During the screening the investigator will evaluate the eligibility of the patients, checking all inclusion and exclusion criteria. Only those patients who meet all inclusion and exclusion criteria will be enrolled in the study. For each JPS implant a unique case number will be assigned (ID), and reported in the eCRF. Considering that each patient can contribute for more than one JPS implant: one patient can have more than one ID. In the eCRF the IDs are linked to the first ID assigned to the same patient by the clinical site. The patients not enrolled for non compliance will be considered as screening failures and will not be entered in the eCRF. Only for the enrolled patient, the Investigator will collect the demographic data and the medical history of the patient including information concerning the limb to be treated with JPS (baseline) such as the radiographic images and clinical examination.

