12.3.2 Safety Variables

The safety profile of JPS will be assessed by the following safety endpoints:

- percentage (%) of subjects (\pm the upper and lower of limit of the 95 % confidence interval) with at least one serious/not serious adverse event surely or possibly related to

JPS (ADEs) (primary safety endpoint). Exact limits will be calculated by Chi-square test with Clopper option.

- percentage (%) of medical device deficiency (secondary safety endpoint). Exact limits will be calculated by Chi-square test with Clopper option.
- percentage (%) of implants where a serious/not serious adverse event certainly related or possibly related to JPS is registered on total surgical implants performed (up to 18 months according to site's standard practice). Exact limits will be calculated by Chi-square test with Clopper option.

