14.2 Monitoring

The sponsor planned to perform a 100% source data verification (SDV), on inclusion/exclusion criteria and on the endpoints variables. On the remaining data the SDV will be performed by random spot check. Before each visit the monitors will contact the investigator/centre to schedule the visit and will send a written confirmation and the related agenda.

In order to fulfill its responsibility of assuring the proper conduct of the study regarding adherence to the CIP and the completeness and accuracy of the data recorded on the case report forms, the sponsor planned to perform at least the following monitoring visits:

- Site Initiation Visit (SIV), to be performed after EC approval;
- 6 monitoring visits throughout the life phase of the study and according monitoring plan;
- Close Out Visit (COV), after the last patient's data are entered into eCRF.

In case of need the investigational site is subjected to additional monitoring visits. The Investigator and/or study staff will be expected to be available for at least a portion of the monitoring visit to answer questions and to provide any missing information.

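### SAP 13 applies one eligibility-filtered set to every analysis, safety included; this departs from the Protocol 12.3.2 implant-level denominator and can remove a treated case's device-related event from the reported rates

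*SAP*

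**What the plan says.** SAP 13 divides implants in two. Those it calls evaluable "are defined as all implants who meet all inclusion criteria and none of the exclusion criteria described in the protocol"; an implant that breaks even one of these conditions is classed as non-evaluable. The section closes with "Analyses will be performed on evaluable implants" and makes no exception. SAP 14 and SAP 23 introduce no safety population, so the adverse event, related-event and deficiency percentages in SAP 23, with their 95.2% Clopper-Pearson intervals, fall under this filter.

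The protocol defines no analysis sets. Its third safety variable in section 12.3.2 is the "percentage (%) of implants where a serious/not serious adverse event certainly related or possibly related to JPS is registered on total surgical implants performed". The primary endpoint in Protocol 6.1 is at subject level: "percentage (%) of subjects with at least one serious/not serious adverse event certainly related or possibly related to JPS (primary endpoint"). No set is named for its denominator.

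Three further passages bear on who can be non-evaluable:

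- Protocol 10.2.1: "Only those patients who meet all inclusion and exclusion criteria will be enrolled in the study". Screening failures are kept out of the eCRF.
- Protocol 14.2: the sponsor plans "100% source data verification (SDV), on inclusion/exclusion criteria and on the endpoints variables".
- SAP 16.1: the disposition summary is to show non-evaluable patients and the reasons, so the SAP expects that some may exist among those included.

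**The concern.** Safety is the primary objective. Screening failures never reach the database, so a non-evaluable implant found there belongs to a case that was enrolled, treated with JPS and recognised later as failing a criterion. Source verification of eligibility is one route to that finding. In the retrospective cohort, follow-up and plate removal are complete before data collection, so any such reclassification comes after the outcome exists. Several criteria are matters of judgement: whether the chart is sufficient, whether the patient is able to comply, and whether some other condition makes the patient ineligible in the investigator's opinion.

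A filter of this kind suits a performance or per-protocol analysis. Applied to safety, it removes a treated case from both numerator and denominator. The event may still appear in a listing, but not in the percentage and interval that are read against the 15% bound.

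**Working it through.** **Inputs.** Expected event rate 3% and 30 subjects (Protocol 12.2); upper limit to be at most 15% (Protocol 12.1); maximum 40 implant cases (Protocol synopsis, SAP 9); final intervals Clopper-Pearson at 95.2% (SAP 14). Event counts and final numbers are assumptions, because the documents cannot give them.

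**Formula.** For x events in n, the upper limit is the 1 − α/2 quantile of a Beta(x + 1, n − x) distribution. At 95.2%, α = 0.048, so this is the 0.976 quantile.

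**The plan's own figure.** 3% of 30 is 0.9, so about one event. For 1/30 the one-sided 95% exact limit is 14.86%, which reproduces the 30. The two-sided 95% limit is 17.22% and the 95.2% limit is 17.35%. That difference is a separate matter. What counts here is that about one event is expected: 0.9 at 30 cases, and 3% × 40 = 1.2 at 40.

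**Effect of reclassifying one case that carries an event** (95.2% upper limits):

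| All enrolled | Upper limit | Evaluable only | Upper limit | Crosses 15%? |
|---|---|---|---|---|
| 1/30 | 17.4% | 0/29 | 12.1% | yes |
| 1/35 | 15.04% | 0/34 | 10.4% | yes |
| 1/36 | 14.6% | 0/35 | 10.1% | no, already below |
| 2/36 | 18.8% | 1/35 | 15.04% | no, stays above |
| 2/37 | 18.3% | 1/36 | 14.6% | yes |
| 2/40 | 17.0% | 1/39 | 13.6% | yes |
| 3/40 | 20.5% | 2/39 | 17.4% | no, stays above |

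For a fixed x the limit falls as n rises, so the table covers the whole range. With 30 to 35 enrolled, losing the only event crosses the bound. With 37 to 40 enrolled, losing one of two events crosses it. With exactly 36 enrolled, neither does. With three or more events, losing one never crosses it within 40.

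**Effect of reclassifying a case without an event.** The limit rises slightly: 2/37 = 18.32% to 2/36 = 18.79%; 1/37 = 14.27% to 1/36 = 14.64%. The filter therefore lowers the result only when the removed case carries an event.

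**Text comparison.** At implant level, Protocol 12.3.2 counts implants performed and SAP 13 counts only those passing every criterion; the two differ whenever one non-evaluable implant exists. At subject level there is no protocol set to compare with, only a SAP filter that the protocol does not mention.

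**The case against.** The strongest defence is the objective itself. Safety is to be assessed for use according to the IFU, and Protocol 7.2 and SAP 9 exclude off-label use. For an implant that proves contraindicated or off-indication, the SAP 13 filter follows that aim. This stands, and it means that off-IFU cases should not simply be merged into the main rate. It does not cover cases dropped only for chart sufficiency, compliance or investigator opinion, which have nothing to do with IFU use.

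A reader might infer that SAP 13 contradicts the protocol's denominator for the primary endpoint. The documents do not support that. The phrase about implants performed belongs to an implant-level variable that carries no primary or secondary label, and it may be meant mainly to set the unit of analysis. The primary endpoint names no set.

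A reader might also infer that outcome-aware exclusion is planned or has happened. Nothing shows this. SAP 13 classifies from Yes/No screening items in the CRF, and if enrolment follows Protocol 10.2.1 the two sets are identical. For prospective patients, monitoring during the study may detect an eligibility failure before any event. Nor do the documents give a figure for how often reclassification occurs or whether the cases affected carry more events.

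Finally, some visibility exists already: reasons in SAP 16.1, listings in SAP 23.1.4 and 23.2.3, and deviations in the study report (Protocol 14.5). But SAP 16.1 promises only numbers and reasons, and SAP 13 may restrict the listings too. None of these restores the percentage or its interval.

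**Conclusion.** The point holds as a departure from the Protocol 12.3.2 implant-level rate and as an unannounced filter on the subject-level primary endpoint. It is conditional on at least one enrolled, implanted case being classed non-evaluable; otherwise every result is unchanged. Where that happens and the case carries a related event, a single reclassification can shift the upper limit by about 3 to 5 percentage points (18.32 − 14.64 = 3.7 for 2/37 to 1/36; 17.35 − 12.07 = 5.3 for 1/30 to 0/29). That is enough to cross 15% in the configurations set out above, but not in all. These sizes rest on assumed counts and on the removed case being an event carrier. A downward bias is possible but not demonstrated. The change is worth making because safety is the primary objective, few events are expected, and much of the eligibility review can take place once outcomes are known.

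**What to change.** In SAP 13, define a safety set: all enrolled subjects and implants in which JPS was applied and whose data may be used under the consent given, whatever later eligibility findings show. Then:

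- Report SAP 23 on this set: adverse events, related events and deficiencies, by patient and by implant.
- Use it for the Protocol 12.3.2 implant-level rate.
- For the subject-level primary endpoint, show it next to the evaluable result, so that cases failing only non-IFU criteria are not lost. Flag off-IFU and contraindicated cases separately, in keeping with the on-IFU objective.
- Keep evaluable implants for SAP 24.
- List each non-evaluable case with its reason and its adverse events and deficiencies.

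The cost is SAP wording and one extra set of tables from data already in the eCRF. The all-implanted rate may come out slightly less favourable. The change does not address patients screened out before entry to the eCRF.
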